APPENDIX C: SITE SURVEY

Hospital-level services	
What is your hospital type?	Tertiary / District (Rural) / District (Non-rural)
How is your hospital funded?	Public / Private / Mixed
Total number of inpatient beds	(Number)
Do you have Level 2 (HDU) or Level 3 (ITU) facilities?	Yes (Number of beds) / No
Do you have a specialised HPB team at your centre	Yes / No If yes: (i) Are there on-call services from them: Every day 24 hour / Everyday, daytime 0800 - 1700 / Weekdays, 24 hour / Weekdays, daytime 0800 - 1700 (ii) Do they have a dedicated pathway for management of bile duct injury: Yes / No If no , are there on-call surgeons specialised in HPB: Within the same city / In other city / In the region / None
Do you have access to minimally invasive surgical equipment?	Yes (Laparoscopic / Robotic) / No If yes , do you routinely take intraoperative images? Yes (Video / Photo) / No
Cholecystectomy services	
What is the approximate total number of cholecystectomies performed each year?	(Number)
What is the number of consultants/ attending surgeons who perform cholecystectomies each year?	(Number)
Which specialist consultants/ attending surgeons perform cholecystectomies each year? (select all that apply)	General / Upper GI / HPB / Colorectal / Breast / Other
What type of services for cholecystectomy services do you provide? (select all that apply)	Elective / Emergency If emergency: 
 What is the approximate total number performed each year? (Number) Do you have dedicated theatres for these services? Yes (Everyday / Once a week / Once every 2 week / More than once every 2 weeks) / No
Where does cholecystectomy get performed on your site? (select all that apply)	Day unit / Elective theatre / Emergency theatre
Have you got access to intraoperative cholangiogram?	Yes - routinely / Yes - selectively / No if yes - selectively or no: What is the supply for these? Good supply / Limited supply / None
Number of consultants / attendings who perform laparoscopic cholecystectomy	(Number)
Do you routinely follow-up after cholecystostomy?	Yes - routinely / Yes - selectively / No

Diagnostic / treatment around gallbladders	
Types of diagnostic imaging available (select all that apply)	Ultrasound (On-site / Off-site) / Computer Tomography (On-site / Off-site) / MRCP (On-site / Off-site) / EUS (On-site / Off-site) / HIDA (On-site / Off-site)
Does your hospital have access to cholecystostomy for gallbladder drainage?	Yes / No If yes , are there on-call services from them: Every day 24 hour / Everyday, daytime 0800 - 1700 / Weekdays, 24 hour / Weekdays, daytime 0800 - 1700 If no , are there on-call surgeons specialised in HPB: Within the same city / In other city / In the region / None
Is there a dedicated ERCP list?	Yes (Everyday / Once a week / Once every 2 week / More than once every 2 weeks) / No
Which of the following services do you have?	Intraoperative cholangiogram / Laparoscopic ultrasound / ICG For each: Routine use / Selective use with good supply / Selective use with limited supply
Do you send gallbladders for histological examination after surgery?	Yes - routinely / Yes - selectively / Not sent for histology / No access to histology
Training in cholecystectomy	
Are there trainees in the department who perform gallbladder surgery?	Yes / No If yes : (i) How many? (Number) (ii) What is their grade? Post-training fellow / Trainee / Non-trainees or doctors
Are there facilities for simulations training for cholecystectomies?	Yes (Local hospital / Regional / National) / No If yes to either , what are the types of simulation training: Box trainer / IT simulation model / Animal model
Are there specific structured educational programmes or coaching for bile duct injury training?	Yes (Local hospital / Regional / National) / No
Green surgery for laparoscopic cholecystectomy	
Are reusable laparoscopic ports used?	Yes (Always / Sometimes) / No / Not available
Are reusable surgical instruments used?	Yes / No / Not available
Are reusable drapes used?	Yes (Always / Sometimes) / No / Not available
Are reusable gowns used?	Yes (Always / Sometimes) / No / Not available
Are reusable scrub caps provided by your hospital?	Yes – routinely / Yes - if requested / No / Not available
Are single-use instruments recycled?	Yes / No / Not available
Are “clean” paper and plastic waste recycled?	Yes / No
Is general anaesthesia given through IV rather than anaesthetic gases for environmental reasons?	Yes – routinely / Yes – occasionally / No / Not available

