2. To assess adverse events following cholecystectomy (e.g., bile duct injury) and their management.
3. To analyse rates and outcomes of unsuspected gallbladder cancer.
4. To evaluate the global variation in the availability of cholecystectomy services and training amongst included hospitals.
5. To assess sustainable practices in laparoscopic cholecystectomy globally.

AUDIT STANDARDS

Pre-operative

1. **Interventional radiology service:** There should be 24-hour access to interventional radiology to support the delivery of an emergency HPB service [11].
2. **Risk Stratification:** For patients with acute cholecystitis, surgeons may use the Tokyo Guidelines 18 (TG18) [8].
3. **Timing of surgery:** In patients presenting with acute cholecystitis, the optimal timing for cholecystectomy is within 48 hours, and no more than 10 days from symptom appearance [7].

Intra-operative

1. **Critical Safety View (CVS):** The use of the CVS during laparoscopic cholecystectomy (achieving all 3 components – Figure 1) is the recommended approach to correctly identify relevant anatomy and minimize the risk of bile duct injuries [7,8]:
 - I. **Clearance of the hepatocystic triangle:** The HC triangle should be cleared of all the fibro-fatty and soft areolar tissue.
 - II. **Exposure of the lower cystic plate:** The gallbladder should be separated from its liver bed to expose at least the lower third of the cystic plate.
 - III. **Only two tubular structures should be seen entering the gallbladder:** the cystic duct and the cystic artery.

[figure not shown]

Figure 1: Photographs showing the critical view of safety.

2. **Intraoperative imaging:** in patients with uncertainty of biliary anatomy or suspicion of bile duct injury, intraoperative imaging (e.g. cholangiogram, laparoscopic ultrasound and incisionless cholangiography with fluorescence) may help delineate relevant anatomy, detect bile duct stones, and decrease the risk of bile duct injury [7,8,12].
3. **Bailout Procedures:** When CVS cannot be achieved and the biliary anatomy cannot be clearly defined by other methods (e.g. imaging) during laparoscopic cholecystectomy, surgeons should

consider a bailout procedure (e.g. subtotal cholecystectomy or total cholecystectomy by the fundus-first (top down) approach) [7].

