- **Return to theatre:** Each patient should only be entered into the study once. Any patient returning to theatre and requiring a cholecystectomy for whatever indication, should not be included.
- **Known gallbladder malignancy:** when the diagnosis of gallbladder cancer is established pre-operatively, the patient should be excluded. However, if gallbladder cancer is found unexpectedly during or after cholecystectomy (i.e. on histology), the patient should be included.

STUDY PROCEDURES

Site Survey

In order to describe local processes and resources, each site will be asked to complete an online site survey questionnaire to delineate the variation of cholecystectomy services and training amongst included hospitals (**Appendix C**).

*Completion of the short site survey can be done by a supervising consultant (preferred) or a hospital lead trainee that is familiar with the cholecystectomy practices at your site. Completion of the site survey is necessary before the site is granted access to the online **GECKO**: Data Collection form.*

Data Collection

Collaborators will collect data on consecutive eligible patient undergoing cholecystectomy within the pre-specified data collection periods (**Table 1; page 15**). Data collectors should use a combination of the **GECKO** Case Report Form (**Appendix A**) alongside the Data Dictionary (**Appendix B**) to successfully record required data on all eligible patients. Collaborators will create clear mechanisms appropriate to their institution to identify and include all eligible patients, involving daily review of operating logbooks, multidisciplinary team meeting, admission and handover lists. Local arrangements may include daily review of the patient and notes focused on included data points.

Data will be collected and stored online via the Research Electronic Data Capture (REDCap) web application (**see pages 20-21**), hosted and managed by the University of Edinburgh, United Kingdom. No patient identifiable data will be uploaded or stored on the REDCap database.

Strategies to identify consecutive eligible patients could include:

- *Daily review of elective theatre lists.*
- *Daily review of handover sheets/emergency admission and ward lists.*
- *Daily review of theatre logbooks (both elective and emergency).*

Follow-up Period

Centres will undertake patient follow-up at two timepoints:

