The secondary endpoints include:

- Rates of achieving a critical view of safety.
- Rates of different bailout procedures initiated when safe cholecystectomy is compromised.
- 30-day and one-year rates of textbook outcomes [2] for cholecystectomy, which covers: postoperative complications (Clavien-Dindo classification), intraoperative complications (including bile duct and vascular injuries), length of stay, readmission, mortality, and postoperative imaging or intervention.
- Unsuspected gallbladder cancer rates and their 30-day and one-year outcome rates, which includes: (1) complication rates (Clavien-Dindo classification); (2) time-to-recurrence rates (time from surgery to recurrence); and (2) revisional surgery rates (liver resection, bile duct resection and/or lymph node dissection).
- A description of the global variation in the availability of cholecystectomy services, training and sustainable practice.

Control of Bias and Confounding

Data will be collected on audit standards and confounding factors for risk-adjusted analyses. These include age, sex, body mass index, American Society of Anaesthesiologists (ASA) grade, and relevant comorbidities. Variables including operative urgency, operative contamination, and operative approach will also be collected. Without appropriately adjusting for risk factors, it is likely that any findings would be biased and unable to be appropriately analysed on an international scale. A full list of required data fields is available in **Appendix B**, and on the REDCap database.

Data Analysis & Sample Size

Variation across different international health settings will be tested using the human development index (HDI) countries [17] a composite statistic of life expectancy, education and income indices published by the United Nations. Initially, data will be reported using descriptive analyses. Comparisons between groups will be undertaken using appropriate parametric and non-parametric analyses. Multilevel logistic regression multivariate models will be constructed to account for case mix, with population stratification by hospital and country as random effects.

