Further prespecified subgroup analyses will be made by operative approach (open, laparoscopic and converted), and operative urgency (elective, emergency and delayed surgery). Audit standards (see pages 9-10) and site survey (Appendix C) will guide exploratory analysis into the global variation in the provision of cholecystectomy and available resources. However, it is acknowledged that some audit standards are designed for high-income settings and therefore their attainment will not be considered mandatory or a potential definitive measure of quality in global cholecystectomy.

Identification of hospital or surgeon-specific performance will not be reported. Following analysis, results will be fed back to participants at the centre level, but no other centres will be identifiable.

Based on previous GlobalSurg studies [14-16], GECKO is anticipated to include around 500 centres globally. With consideration to recent figures provided by previous collaborative studies [3,5] on cholecystectomy, a sample of approximately 15000 patients is anticipated. The recent multi-society practice guidelines on prevention of bile duct injury [8] advised that a study adequately powered to detect and report on bile duct injury would require at least 9000 patients.

DATA GOVERNANCE

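### Site survey: the frequency options for dedicated emergency theatres and ERCP lists are neither exclusive nor exhaustive, so frequent and infrequent services can share one code

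*Protocol*

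**What the plan says.** Appendix C asks hospitals that provide emergency cholecystectomy whether they have dedicated theatres for it. Later, under diagnosis and treatment, it asks "Is there a dedicated ERCP list". Both items offer "Yes (Everyday / Once a week / Once every 2 week / More than once every 2 weeks) / No". Neither the appendix nor the study definitions in Appendix D explains the last positive option.

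Under the cholecystectomy services heading, the only survey question on follow-up reads "Do you routinely follow-up after cholecystostomy". The next part of the survey asks "Does your hospital have access to cholecystostomy for gallbladder drainage".

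The survey has a stated role:

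- Study Procedures (Site Survey) gives its purpose as to "delineate the variation of cholecystectomy services and training amongst included hospitals".
- Secondary aim 4 is "To evaluate the global variation in the availability of cholecystectomy services and training amongst included hospitals".
- The matching secondary endpoint is "A description of the global variation in the availability of cholecystectomy services, training and sustainable practice".
- Data Analysis & Sample Size says that the audit standards and the survey "will guide exploratory analysis into the global variation in the provision of cholecystectomy and available resources".

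**The concern.** A frequency scale is useful only if each respondent has exactly one fitting answer and the codes can be ordered. Here the first three positive options descend from daily to weekly to fortnightly. The reader then expects a category for services rarer than fortnightly, but the words describe services more frequent than fortnightly. Sites at either margin may choose this option: those running lists several times a week because the words fit, and those running lists monthly because the position fits.

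If that happens, the code mixes frequent and infrequent services, and nothing else in the survey separates them afterwards. The response options are fixed in the protocol's own appendix, and no analysis plan can recover a frequency that was never recorded. At stake is the description of how often hospitals provide these two services, and any exploratory comparison that uses that frequency.

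The follow-up item raises a smaller question. Its heading and neighbouring items concern cholecystectomy, but it names a drainage procedure. If cholecystectomy was meant, the survey does not ask about routine follow-up after the study operation, although the Follow-up Period section ties outcome ascertainment to each hospital's routine practice.

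**Working it through.** No sample size, power or error rate is involved, and the plan states no figure to reproduce. The check places plausible service frequencies on the printed scale.

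**Inputs.** The options come from Appendix C. The service frequencies are illustrative assumptions, because the protocol gives no distribution across sites.

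**Common unit.** Sessions per 14 days = 14 × (sessions ÷ days in the cycle). For example, two a week gives 14 × 2/7 = 4, every three weeks gives 14 × 1/21 = 0.67, and every four weeks gives 14 × 1/28 = 0.5.

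**Two readings of the last option.** Literal: rate above 1 per 14 days. Positional: gap longer than 14 days, that is, a rate below 1.

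| Service | Sessions per 14 days | Has its own option | Fits last option, literal | Fits last option, positional |
|---|---|---|---|---|
| Daily | 14 | yes | yes | no |
| Weekdays only | 10 | no | yes | no |
| Three a week | 6 | no | yes | no |
| Two a week | 4 | no | yes | no |
| Weekly | 2 | yes | yes | no |
| Fortnightly | 1 | yes | no | no |
| Every three weeks | 0.67 | no | no | yes |
| Every four weeks | 0.5 | no | no | yes |

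**Result, literal reading.** Daily and weekly services each fit two options, so the scale is not exclusive. Services at 0.67 or 0.5 have no positive option, so it is not exhaustive.

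**Result, positional reading.** No service fits two options, but those at 4 to 10 sessions per 14 days have none. The survey's on-call items distinguish every day from weekdays, so weekday-only provision is a pattern that the designers had in mind.

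**Result, sites differing in their reading.** The last code can hold a two-a-week service and a four-weekly one (4 ÷ 0.5 = 8-fold apart), or a weekday service and a four-weekly one (10 ÷ 0.5 = 20-fold apart).

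**Reach.** None of the pre-, intra- or post-operative audit standards uses theatre-session or ERCP-list frequency. The regression models in Data Analysis & Sample Size are described as adjusting for case mix, with hospital and country as random effects; list frequency is not named in them.

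**Follow-up item.** Cholecystostomy appears on purpose elsewhere: in the survey's access item, and in the case report form and data dictionary as an option when cholecystectomy is not performed. The wording could therefore be deliberate. If so, the item precedes the access question, is not conditional on it and has no not-applicable answer. A hospital without cholecystostomy can then answer only no, the same as one that drains gallbladders but does not follow up routinely.

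**The case against.** The strongest reply is that this is a wording matter with limited reach, and much of that stands. The endpoint is descriptive and the further use is exploratory. Most of the survey (beds, specialist cover, imaging, training, sustainability) is untouched. Availability, which is what the aim and endpoint name, can still be reported as yes or no.

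A reader might infer that the best- and worst-served hospitals fall into one code. The documents do not support that: a daily service has its own option and a hospital with no dedicated service can answer no. The mixing concerns services between weekly and daily on one side and below fortnightly on the other. It also requires sites to read the option differently, so it is a risk and not a certainty. The risk is real, since about 500 self-reporting centres are expected and the protocol is to be translated into several languages.

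A reader might also infer that the follow-up item certainly names the wrong procedure, or that follow-up practice is otherwise unrecorded. Neither is established. Cholecystostomy is a deliberate item elsewhere, and the Data Validation section has every hospital self-report its methods for determining 30-day outcomes. That self-report, as described, does not extend to one-year outcomes.

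The reply does not remove the defect in the scale. Under each reading, some ordinary service pattern has no fitting positive answer.

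**Conclusion.** The concern holds in a limited form. The shared frequency scale is defective in two survey items, and those items may be misclassified in the descriptive secondary endpoint on service availability and in exploratory analyses. The documents do not support the stronger conclusion that between-site comparisons of services in general will be wrong, and the primary endpoint is not affected.

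The size cannot be given as a number of centres. That would need the distribution of list frequencies and the way sites read the option, and the protocol gives neither. The theatre frequency is also asked only of hospitals offering emergency cholecystectomy. The 8-fold and 20-fold contrasts show how unlike two sites in the same code could be; they rest on assumed frequencies and say nothing about how often this happens.

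On the follow-up item, a slip is probable from its heading and neighbours but not proven. Only a request to confirm the intended procedure is supported.

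**What to change.** In both items use exclusive, ordered options: Every day / 2-6 times a week / Once a week / Once every 2 weeks / Less often than every 2 weeks / No.

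The survey must be completed before a site gains access to the data collection form, so answers may already exist. In that case, ask every site that gave a positive answer other than the daily one to confirm its frequency as it stood during the data collection period. Asking only those that chose the last option would miss sites that settled for a neighbouring one. The alternative is to analyse the two items as yes/no only, which keeps availability and gives up frequency. Neither route catches a site that answered no because nothing fitted.

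Confirm which procedure the follow-up item means. If cholecystectomy, correct the word. If cholecystostomy, move the item beside the access question and add a not-applicable answer.

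The cost is the wording of three survey items and, where surveys are in, a short query to the hospital lead.

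### In the site survey, hospitals without cholecystostomy are asked about HPB surgeons instead of drainage elsewhere, and the two on-call schedule lists have no code for no on-call service

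*Protocol*

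**What the plan says.** The site survey (Protocol, Appendix C) holds two items built on the same pattern.

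- Under hospital-level services: "Do you have a specialised HPB team at your centre". A Yes leads to "Are there on-call services from them: Every day 24 hour / Everyday, daytime 0800 - 1700" and two weekday patterns. A No leads to "are there on-call surgeons specialised in HPB: Within the same city / In other city / In the region / None".
- Under diagnosis and treatment around gallbladders: "Does your hospital have access to cholecystostomy for gallbladder drainage". A Yes leads to "are there on-call services from them", with the codes "Every day 24 hour / Everyday, daytime 0800 - 1700 / Weekdays, 24 hour / Weekdays, daytime 0800 - 1700". A No leads to exactly the same HPB-surgeon question as in the first item.

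The survey serves secondary aim 4 (Study Aims), "To evaluate the global variation in the availability of cholecystectomy services and training amongst included hospitals", and the matching secondary endpoint (Secondary Outcome Measures), "A description of the global variation in the availability of cholecystectomy services, training and sustainable practice". The Data Analysis & Sample Size section uses it to guide exploratory analysis. Under Study Procedures, a site must complete the survey before it gets access to the data collection form. Under Authorship, completing it is a condition of authorship.

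**The concern.** There are two separate faults in the instrument.

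1. **Wrong subject.** The No branch of the cholecystostomy item does not concern cholecystostomy. A hospital without the service is asked about specialist surgeons and is never asked where drainage could be obtained.
2. **Missing code.** The Yes branches of both items assume that a service that exists also has on-call cover. A hospital with the service but no on-call arrangement has no true answer to give.

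What is at stake is how well the study can describe service availability across settings. Neither fault can be repaired in the analysis, because an answer that was never asked for, or that could not be given, cannot be recovered afterwards.

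**Working it through.** The protocol states no figure to reproduce, and no formula applies. The check sets the two items side by side.

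| Element | HPB-team item | Cholecystostomy item |
|---|---|---|
| Stem | Team present, Yes/No | Access to cholecystostomy, Yes/No |
| Yes branch, subject | On-call services from the team | The same wording, with no team in the stem to refer to |
| Yes branch, codes | Four positive schedules, no negative code | The same four, no negative code |
| No branch, subject | Location of on-call HPB surgeons | The same text, word for word |
| No branch, codes | Three locations plus None | The same |
| Does the No branch fit the stem? | Yes | No |

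**Step 1: the wrong-subject branch.** The No branches are identical. The Yes branch of the cholecystostomy item also keeps a pronoun, "are there on-call services from them", that points to a team in the first item and to nothing in the second. Both signs suggest that text was carried over from one item to the other. It is complete and grammatical, so broken text extraction does not explain it. For a hospital answering No on cholecystostomy:

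- If it also has no HPB team, it answers the same question twice.
- If it has an HPB team, it is asked for the location of on-call HPB surgeons with no option for its own site.
- In both cases the location of the nearest drainage service goes unrecorded.

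The imaging item in the same section separates on-site from off-site provision, so the survey does record provision elsewhere for related services.

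**Step 2: the missing code.** Appendix C has four on-call questions: a Yes branch and a No branch for each of two items. The two No branches include None. The two Yes branches do not. The gap therefore affects 2 of 4. Neighbouring items on dedicated emergency theatres and dedicated ERCP lists pair their frequency options with a plain No, so the omission departs from the survey's own practice.

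**Step 3: who is miscoded.** Among hospitals that have the service:

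- 24-hour cover, every day or on weekdays: a correct code exists.
- Daytime-only cover, every day or on weekdays: a correct code exists.
- No on-call arrangement at all: no correct code exists.

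Only the last group is affected. A false tick overstates its cover. A blank cannot be told apart from an unanswered question.

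**Step 4: number of centres.** The protocol anticipates about 500 centres but gives no share without cholecystostomy and no share lacking on-call cover. If a share *p* answers No on cholecystostomy, 500 × *p* centres lose the follow-on, which is 500 × 0.10 = 50 centres for each 10 percentage points. This is a scale only; *p* is unknown.

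**The case against.** The strongest reply is that little is lost. The stem asks about access, so a No already records that access is lacking, which is what aim 4 needs. No aim or endpoint asks for the location of the nearest alternative. The HPB-surgeon branch is plainly labelled, and nothing in the protocol says it will be reported as drainage access. The survey supports a descriptive endpoint and exploratory work, and the online form actually used is not shown and may differ from Appendix C.

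Much of this stands, and it rules out several stronger readings that a reader might infer:

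- *That the study will hold no information on drainage access, or mis-measures services where they are poorest.* The stem captures lack of access, and the missing code affects only hospitals that have the service.
- *That cover is overstated wherever there is no out-of-hours service.* The daytime codes describe that situation correctly.
- *That on-call questions in general lack a negative code.* Two of the four include None.
- *That a definite number of centres is affected.* Any such figure needs a share that the protocol does not give.
- *That the primary endpoint is compromised.* The audit standards ask for 24-hour interventional radiology, and Appendix C has no item naming it, so the cholecystostomy schedule is the nearest proxy. But the protocol does not say that this item scores the standard. A site without on-call cover that ticked a daytime code would still be recorded as not having 24-hour cover.

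The reply does not remove the faults themselves. The follow-on has the wrong subject for its stem, and some hospitals cannot answer truthfully in a survey they must complete to take part.

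**Conclusion.** The point holds in a limited form. As printed, Appendix C asks one follow-on about the wrong service, so access to drainage elsewhere is not recorded for hospitals without cholecystostomy. Two of its four on-call questions cannot record the absence of on-call cover among hospitals that have the service. The effect falls on the descriptive secondary endpoint for service availability and on the exploratory analyses. No effect on patient outcomes, the risk-adjusted models or the primary endpoint is shown. The number of centres affected is unknown. The conclusion assumes that the deployed survey matches Appendix C, which the sponsor should confirm. The faults are modest but worth correcting, because the repair is small and no later analysis can supply the missing answers.

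**What to change.** Make three changes to Appendix C and to the online form:

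1. Reword the No branch of the cholecystostomy item to ask where the nearest cholecystostomy or gallbladder drainage service is, keeping the survey's existing location codes (same city, other city, region, none).
2. In the Yes branch of that item, replace the pronoun so that the question asks about on-call services for cholecystostomy.
3. Add a code for no on-call service to the Yes lists of both the HPB-team and the cholecystostomy items.

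If surveys have already been returned, do not report the No branch of the cholecystostomy item as drainage access. Report the on-call results with the caveat that absence of on-call cover could not be recorded.

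The cost is a few words in the survey, with no change to patient-level data. Because sites complete the survey before gaining access to the data form, those that have already answered would need a short re-query, or the caveat would have to stand for them.
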